6.2. AEs

AEs will be documented on the AE CRF and monitored continuously throughout the study from the time of informed consent until 30 days after the patient's last MIRV or until the event has resolved, stabilized, or returned to baseline. AEs attributed to study procedures, including those events that occur prior to the first dose, should also be documented on the AE CRF.

AE data are available to ImmunoGen from 2 sources, the clinical database and the serious adverse event (SAE) forms. While reconciliation will be performed, the production of data summaries and listings will be based on the data collected on the clinical database.

Pre-treatment AEs are defined as AEs with an onset date prior to the first dose of MIRV. TEAEs are defined as AEs with an onset date on or after the first dose of MIRV, and within 30 days of the last dose of MIRV or prior to the start of a new anti-cancer treatment, whichever occurs first. Medical history conditions that exist before the initiation of MIRV but worsen in severity during the study will also be recorded on the AE CRF as an AE and will be included as treatment-emergent in the summary tables and listings.

The adverse events will be coded using MedDRA (Version 24.0), associating lower-level terms with PT and SOC by the primary hierarchy. The tables will display the counts and percentages of patients who reported at least 1 TEAE in each SOC represented in the AE data. Within each SOC, the tables will display the counts and percentages of patients reporting at least 1 TEAE as designated by the PT.

AEs are graded using CTCAE Version 5.0. AE summaries may include summaries for all AEs and by the maximum CTCAE grade for the item being summarized (ie, SOC or PT). In these cases, the outputs will include a row for All Grades as well as rows for the 5 potential CTCAE grades, Grade 1 (Mild), Grade 2 (Moderate), Grade 3 (Severe), Grade 4 (Life threatening or disabling), or Grade 5 (Death). AEs missing a severity grade will not be included in the Grade 1-5 rows of the tables. An AE reported by a patient more than once will be represented in the most severe category. TEAEs will be categorized as MIRV-related if "Possibly Related", "Probably

Related", or "Definitely Related" is selected by investigator. AEs missing relationship to MIRV will be included in the Related TEAE tables and listings.

The following summary tables will be produced:

- An overall summary of safety will summarize the numbers of patients with TEAEs of each grade and the number of patients who died during the study or within 30 days of last dose.
- All TEAEs.
- Serious TEAEs.
- Non-Serious TEAEs (ie, TEAEs excluding SAEs).
- Grade 3 or higher TEAEs.
- TEAEs leading to drug withdrawal. This subset includes TEAEs with an action taken of drug permanently discontinued.
- Related TEAEs leading to drug withdrawal. This subset includes TEAEs related to MIRV with an action taken of drug permanently discontinued.
- TEAEs related to MIRV.
- Serious, related TEAEs.
- TEAEs leading to dose modifications (dose reduction or dose delay).
 - TEAEs leading to dose reduction.
 - TEAEs leading to dose delay.
 - TEAEs leading to dose reduction or dose delay.
- Related TEAEs leading to dose modification (dose reduction or dose delay).
 - Related TEAEs leading to dose reduction.
 - Related TEAEs leading to dose delay.
 - Related TEAEs leading to dose reduction or dose delay.
- Deaths on study treatment or within 30 days of the last dose. This table includes all deaths during study treatment or within 30 days of the last dose, regardless of cause of death.
- TEAEs leading to death. This table includes all TEAEs with CTCAE Grade 5.
- Related TEAEs leading to death. This table includes all TEAEs related to MIRV with CTCAE Grade 5.

The following listings will be produced:

- All pre-treatment AEs will be listed.
- All AEs, sorted chronologically by patient. This listing includes SOC, PT, onset and end dates, and other relevant information.

- Serious TEAEs, sorted chronologically within patient.
- TEAEs leading to drug withdrawal. This subset includes TEAEs with an action taken of drug permanently discontinued.
- TEAEs leading to dose reduction or dose delay.
- TEAEs related to MIRV.
- Serious TEAEs related to MIRV.
- TEAEs resulting in death. This listing includes TEAEs with a CTCAE grade of Grade 5 (death).
- All deaths, with an indication of whether the death occurred on study or within 30 days of the last dose.

The following groupings of TEAEs will be generated as part of the focused analysis of safety:

- Ocular TEAEs.
 - A list of PTs for ocular AEs will be provided and finalized by the Sponsor before the final database lock.
- Peripheral neuropathy TEAEs.
 - A list of PTs for peripheral neuropathy AEs will be provided and finalized by the Sponsor before the final database lock.
- Pneumonitis.

For each of the focused safety analysis groups, the following summary tables will be produced:

- TEAEs by SOC, PT, and maximum CTCAE grade.
- Related TEAEs by SOC, PT, and maximum CTCAE grade.
- Serious TEAEs by SOC, PT, and maximum CTCAE grade.
- Related serious TEAEs by SOC, PT, and maximum CTCAE grade.
- TEAEs leading to discontinuation.
- TEAEs leading to dose reduction or dose delay.
- TEAEs leading to dose reduction.
- TEAEs leading to dose delay.
- Related TEAEs leading to discontinuation.
- Related TEAEs leading to dose reduction or dose delay.
- Related TEAEs leading to dose reduction.
- Related TEAEs leading to dose delay.

Additionally, a table will be produced which contains the following for each of the focused safety analysis groups:

- The number of patients with at least 1 TEAE in each group, presented by treatment arm.
- Time to first onset of each group of TEAEs.
- Action taken with MIRV with respect to each group of TEAEs.

For the focused safety analysis, the following listings will be produced:

- Ocular TEAEs.
- Peripheral neuropathy TEAEs.
- Pneumonitis TEAEs.

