Procedure	Pre-screening	Screening	Cycle 1 C=3 weeks		C2+	C3	EOT	30-Day Follow-up	Survival Follow-up
			D1	D8	D1	D8	≤ 7d from discon.	30 (+14) days from last dose	Every 3 months (±1 month) from EOT
Blood sample for Biomarkers	•	•							
Pregnancy Test ⁱ		• ⁱ	• ^f		•			•	
Ophthalmic Exam ^j		• ^c	Every other cycle from time treatment-emergent eye disorder first reported				• ^j	• ^j	
Ocular Symptom Assessment ^k		• ^c	•		•		•	•	
Radiologic Tumor Assessment ^l		• ^a	Every 6 (±1) weeks from C1D1 for first 36 weeks, then every 12 (±3) weeks				• ^m	• ^m	
CA-125 ⁿ		• ^c	Collect at each radiologic tumor assessment (± 4 days)				• ^m	• ^m	
MIRV administration			•		•				
Record AE/SAEs and concomitant medications	• ^o	•	Collected continuously while patients are on study						
Blood sample for PK ^p			•	•	• ^p	•	•	• ^p	
Blood samples for immunogenicity ^q			•		•		•	•	
Survival Phone screen, including new anticancer therapy ^r									•

Abbreviations: AE = adverse event; aPTT = activated partial thromboplastin time; C = cycle; CA = cancer antigen; D = day; ECOG = Eastern Cooperative Oncology Group; ECG = electrocardiogram; EOT = End of Treatment; FFPE = formalin-fixed-paraffin-embedded; INR = international normalized ratio; PK = pharmacokinetics; PT = prothrombin time; SAE = serious adverse event.

Note: A patient's *BRCA* mutational status (germline or somatic mutation in tumor tissue) will be collected as part of her medical history if available. Patients without a known mutation will be classified as unknown.

- ^a Must be within 28 days before C1D1 unless otherwise specified.
- ^b ECG assessment may be performed predose at C1D1 if not performed previously up to 28 days prior to first dose of MIRV.
- ^c Must be within 14 days before C1D1.
- ^d Testing for FR α expression is required for all patients. Those who do not have archival tumor tissue to submit will be required to undergo procedures to obtain a new biopsy using a low-risk, medically routine procedure during the Pre-screening period to confirm eligibility. If the archival tumor tissue does not meet FR α criteria, a new biopsy tumor sample may be submitted and used to confirm this criterion.
- ^e Complete physical examination (PE) is required at Screening and the 30-Day Follow-up visit. At all other study visits while on MIRV, patients will have symptom-directed PEs.

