8. ASSESSMENT OF SAFETY

8.1. Recording Adverse Events and Serious Adverse Events

Adverse Events (AEs), including those attributed to study procedures, will be documented in the clinical trial database and monitored continuously throughout the study from the time of informed consent until 30 days after the patient's last study treatment.

Only AEs/SAEs which are considered related to a study procedure (ie blood draw or fresh tumor biopsy) will be captured during the pre-screening period, ie from the time of signing of the pre-screening informed consent (if one is utilized) until the time of signing of the main study informed consent, or until the patient is determined to be a screen failure. All AEs and SAEs, regardless of causality, will be captured after the main study ICF has been signed.

SAEs will continue to be followed by ImmunoGen Pharmacovigilance until resolution, stabilization or return to baseline. Beyond this defined reporting period, any unsolicited SAE assessed as related to the study drug by the Investigator and reported to ImmunoGen will be collected and processed. Additional information obtained after database lock, will reside solely in the safety database.

The Investigator should follow and provide updates for all AEs until clinical recovery is complete, laboratory values return to normal, the patient stabilizes, or death occurs, to ensure the safety of the patients. This may mean that observations continue beyond the last planned visit per protocol and that additional investigations may be requested by the Sponsor.

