8.1.1. Definition of Adverse Events

8.1.1.1. Adverse Event

An AE is any noxious, pathologic, or unintended change in anatomical, physiologic, or metabolic function as indicated by physical signs, symptoms, or laboratory changes occurring in any phase of a clinical study, whether or not considered study drug-related. This includes an exacerbation of a pre-existing condition. AEs include:

- Worsening (change in nature, severity, or frequency) of conditions present at the onset of the study
- Intercurrent illnesses
- Drug interactions
- Events related to or possibly related to concomitant medications
- Abnormal laboratory values (this includes significant shifts from baseline within the range of normal that the Investigator considers to be clinically important)
- Clinically significant abnormalities in PE, vital signs, and weight

Note that PD should not be reported as an AE unless it is considered to be drug-related by the Investigator.

All AEs, including AEs attributed to study procedures, occurring from the time of study informed consent until 30 days after last study treatment must be reported in the clinical database, regardless of the severity or relationship to study drug. Only AEs which are considered related to a study procedure (ie blood draw or fresh tumor biopsy) will be captured during the pre-screening period, ie from the time of signing the pre-screening consent (if one is utilized) until the signing of the main study informed consent, or until the patient is determined to be a screen failure. The Investigator should treat patients with AEs appropriately and observe them at

suitable intervals until the events stabilize, return to baseline or resolve. AEs may be discovered through observation or examination of the patient, questioning of the patient, complaint by the patient, or by abnormal clinical laboratory values.

In addition, AEs may also include laboratory values that become significantly out of range. Such abnormal laboratory values or test results constitute AEs if they induce clinical signs or symptoms, are considered clinically significant (eg, cause study drug discontinuation or constitutes in and of itself an SAE, or require therapy), and should be recorded in the clinical database under the signs, symptoms or diagnosis associated with them. In the event of an out-of-range value, the laboratory test should be repeated until it returns to normal or baseline or can be explained and the patient's safety is not at risk.

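### SAP 6.2 dates AEs by onset alone and applies its worsening rule only to medical history, so a screening-period AE that worsens on MIRV can miss the TEAE tables if it stays on one record

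*SAP*

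**What the plan says.** SAP 6.2 splits adverse events at the first dose. On one side: "Pre-treatment AEs are defined as AEs with an onset date prior to the first dose of MIRV". On the other: "TEAEs are defined as AEs with an onset date on or after the first dose of MIRV", up to an end point that is "within 30 days of the last dose of MIRV or prior to the start of a new anti-cancer treatment, whichever occurs first". Neither sentence mentions a change in grade.

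One further sentence deals with worsening. It makes treatment-emergent those "Medical history conditions that exist before the initiation of MIRV but worsen in severity during the study", and says that they are entered on the AE form as well.

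The planned output differs between the two classes. For the first, SAP 6.2 says "All pre-treatment AEs will be listed". The summary tables of that section, apart from deaths, are restricted to TEAEs.

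On collection, Protocol 8.1 says: "All AEs and SAEs, regardless of causality, will be captured after the main study ICF has been signed". Main consent may precede dosing by up to four weeks (Protocol Table 2, footnote a: "Must be within 28 days before C1D1 unless otherwise specified"). Protocol 8.1.1.1 includes among AEs: "Worsening (change in nature, severity, or frequency) of conditions present at the onset of the study".

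**The concern.** Between main consent and first dose, an event goes onto the AE form. It is therefore not plainly one of the medical-history conditions to which the worsening sentence applies, and its onset date puts it on the pre-treatment side. If it later becomes more severe on MIRV, nothing in SAP 6.2 reclassifies it.

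TEAEs are a named secondary endpoint (Protocol 2.2.3; SAP 2.1.3.2.1). The study has one arm, so absolute TEAE rates are the safety result, and no control group is subject to the same rule. Two patients with the same course on drug could be tabulated differently only because one symptom began shortly before the consent signature and the other shortly after.

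**Working it through.** The plan gives no figure that depends on this definition, so there is nothing to reproduce. The check applies the SAP 6.2 wording to three test records.

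Inputs:
- Start rule: onset on or after first dose (SAP 6.2).
- End rule: 30 days after last dose, or start of new anti-cancer treatment if earlier (SAP 6.2). Even a patient dosed only on Day 1 has a window to Day 1 + 30 = Day 31, so Day 30 lies inside it if no new anti-cancer treatment has begun.
- Worsening rule: medical-history conditions only (SAP 6.2).
- AE capture: all causes from main consent (Protocol 8.1).

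| Test record | Class under SAP 6.2 | Class under the fix |
|---|---|---|
| A. AE starts Day -10 at Grade 1, reaches Grade 3 on Day 30, one record | Pre-treatment | TEAE |
| B. Same course, worsening entered as a new record dated Day 30 | TEAE | TEAE |
| C. Medical-history condition, same worsening on Day 30 | TEAE | TEAE |

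A, B and C are the same clinical course on drug. A differs from B only in how the site keeps its records, and from C only in whether the condition is held as an AE or as history.

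No other rule was found that rescues A:
- SAP 3.3 imputes partial onset dates to decide treatment emergence. It is silent on grade changes.
- SAP 6.2 says how to count an event that a patient reports more than once. It does not say that a worsening becomes a second report or takes a new date.
- SAP 6.2.1 tabulates events near a fresh biopsy whether or not they are TEAEs, but only within 7 days of the biopsy.

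What still shows A:
- The pre-treatment and all-AE listings (SAP 6.2).
- Laboratory grade shifts and worst grades (SAP 6.3), if the event is a laboratory one.
- Visual acuity, intraocular pressure and cataract shifts (SAP 6.8), if it is one of those.
- The all-cause table of deaths on treatment or within 30 days of last dose (SAP 6.2), if it is fatal.

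Symptomatic events such as nausea, pain or fatigue have no equivalent table.

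Size: one patient is 1/110 = 0.9 percentage points. The documents give no rate for such events. As an assumption only, if 1% to 5% of patients had one, the count would be 110 × 0.01 = 1.1 to 110 × 0.05 = 5.5, or about 1 to 6 patients. A patient with any other TEAE is already in the overall row, so the effect would fall mainly on the preferred-term, Grade 3 or higher, serious and action-taken rows.

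**The case against.** The strongest reply is that the loss depends on a document we do not have. If the CRF completion instructions open a new record at each grade increase, record B applies and nothing is lost. Protocol 8.1.1.1 can be read that way, since it treats exacerbation of a pre-existing condition as an AE in its own right, which could carry a post-dose onset date. This stands as a condition on the finding. It does not remove it: that section speaks of conditions present at study onset and does not say how to date or re-enter an AE already on the form.

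A second reply is that the worsening sentence is anchored to conditions existing before MIRV, not before consent, and that Protocol 7.5 has medical history compiled during screening with no cutoff at consent. A screening-onset condition might then be held as history and be covered. That is possible. But Protocol 8.1 requires such an event to be captured as an AE, and the SAP's statement that history conditions are entered on the AE form as well implies that they were not there already.

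Third, eligibility limits what can be lost from the focused tables. Corneal disorders, neuropathy above Grade 1 and previous noninfectious pneumonitis are excluded (Protocol 3.1.2, items 6, 5 and 12), and prior-therapy toxicities must have stabilized or recovered (Protocol 3.1.1, item 11). A reader might infer that the ocular, neuropathy and pneumonitis tables are materially distorted. They use the same TEAE rule, but the documents do not support that inference.

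A reader might also infer a second error in the other direction: the history clause refers to worsening during the study, which could include worsening after consent but before any drug. The clause is loosely worded, but the sentence on pre-treatment events already assigns a pre-dose onset to that class. It merits tidying and is not a separate defect.

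**Conclusion.** The definition should be corrected before database lock. As written, it gives the wrong class to an AE that begins between main consent and first dose, worsens on MIRV within the TEAE window, and is kept on one record. Such an event is listed but misses the TEAE tables for all events, Grade 3 or higher, serious, related, dose modification and withdrawal.

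The conclusion rests on one assumption, single-record capture, which the documents neither require nor rule out. They therefore do not support saying that every such event drops out, nor do they support a particular patient count or a claim that these events are common in screening. Where the loss occurs, it understates on-drug severity in the TEAE tables. The number is unknown and, with at most about four weeks between main consent and dosing, probably small. The primary ORR analysis and the deaths table are not affected.

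**What to change.** In SAP 6.2:
- Define a TEAE as an AE with onset on or after first dose, or any AE or medical-history condition present before first dose that increases in CTCAE grade on or after first dose, in either case within the existing end-of-window rule.
- Tabulate such an event at the grade reached on or after first dose.
- In the medical-history sentence, replace *during the study* with *on or after the first dose*, so that worsening before any drug is clearly pre-treatment.

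In the CRF completion guideline, require a grade increase after dosing to be recorded with its own date. Without that date the rule cannot be programmed reliably.

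The cost is a short SAP revision, which SAP 1.1 allows before final database lock, plus one programming rule and one guideline line. If grade changes have not been dated so far, sites would need queries on AEs that began before first dose and continued past it. The reported TEAE rate may rise slightly.

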Abbreviations: CTCAE = common terminology criteria for adverse events; ANC = absolute neutrophil count; PLT = platelets; CT = computed tomography; AE = adverse event.

^a Failure to meet retreatment criteria within 1 cycle (21 days) after the missed dose due to insufficient recovery from a treatment-related toxicity will result in treatment discontinuation unless otherwise specified in the management guidance for a particular toxicity.

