5.5.2.2. Management and Dose Modification Guidelines

If a patient develops ocular symptoms of any grade, the patient is required to have a complete examination by an ophthalmologist. If a patient develops \geq CTCAE Grade 2 ocular symptoms, treatment with MIRV must be interrupted. Treatment should not be interrupted solely for Grade 2 ocular signs (eg, Grade 2 keratopathy) unless they are also associated with Grade 2 ocular symptoms. Treatment with MIRV may resume if ocular symptoms improve to Grade 1 or baseline within 28 days of the next scheduled MIRV dose (refer to [Table 5](#) for details). If ocular

symptoms last longer than 28 days, resumption of MIRV, with or without dose reduction, may be considered for those patients who have experienced clinical benefit if agreed upon between the Sponsor and the Investigator. Subsequent eye examinations will be scheduled to occur in every other cycle going forward, from the time that the AE was initially reported, and at either the EOT visit or 30-Day Follow-up Visit after treatment discontinuation, even if the results of the patient’s ocular exam shows no obvious clinical findings. Management of treatment-emergent ocular AEs with inflammatory characteristics should include corticosteroid eye drops and/or other measures as indicated by an ophthalmologist.

Table 5: Management of Ocular Symptoms

Severity Grade (CTCAE v5.0)	Management	Guidelines for MIRV Dose Modifications
Grade 1	Complete eye exam as outlined in Schedule of Assessments (Table 2) Monitor for worsening symptoms	Continue MIRV dosing
Grade 2	Complete eye exam as outlined in Schedule of Assessments (Table 2) Repeat complete exam as clinically indicated Patients should have weekly symptomatic ocular assessments by the Investigator until the symptoms resolve to Grade 1 or baseline or are deemed to be irreversible by the Investigator	Hold MIRV dosing until AE has resolved to Grade 1 or better Patients with ocular symptoms lasting < 14 days may be allowed to resume MIRV at the same dose level Patients with ocular symptoms lasting ≥ 14 days but no more than 28 days may resume MIRV at one lower dose level Recurrence of Grade 2 toxicity on subsequent cycles despite best supportive care will require a MIRV dose reduction of one dose level

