5.6. Discontinuation of the Patients from the Study or Study Treatment

5.6.1. End of Treatment

Patients will continue to receive MIRV until they present with PD per RECIST 1.1, as assessed by study Investigator, unacceptable toxicity, withdraw consent, or death, whichever comes first, or until the Sponsor terminates the study. Study treatment and/or participation in the study may be discontinued at any time at the discretion of the Investigator. The following may be reasons for the Investigator to remove a patient from the study drug:

- The patient suffers an intolerable AE
- Noncompliance, including failure to appear at one or more study visits
- The patient was erroneously included in the study

The reason for treatment discontinuation must be captured in the clinical trial database. Any AEs experienced up to the point of discontinuation and 30 days thereafter must be documented. All serious adverse events (SAEs), and those AEs assessed by the Investigator as at least possibly related to study drug should continue to be followed until they resolve or stabilize, whichever comes first. Patients will continue to be followed for OS, after discontinuing study drug ([Section 9.3.3](#)).

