5.7. Period of Observation

For purposes of this study, the period of safety observation extends from the time of informed consent until the 30-Day Follow-up visit unless additional follow-up safety information is requested as described in [Section 9.3](#). Short-term follow-up for patients who discontinue study drug without documented PD will be followed per RECIST 1.1 every 6 weeks (\pm 1 week) from C1D1 for the first 36 weeks then every 12 weeks (\pm 3 weeks) until PD, until the patient starts new anticancer treatment, the patient dies, or the patient withdraws consent, whichever comes first. All patients will be followed every 3 months (\pm 1 month) for survival until death, lost to follow-up, withdrawal of consent for survival or until EOS, whichever comes first.

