9.3. Follow-up Assessments

9.3.1. 30-Day Follow-up Visit

A 30-Day Follow-up visit will occur 30 days (+14 days) after last dose of MIRV and should occur prior to the start of new anticancer therapy.

In some cases, nonserious AE observations may continue beyond the safety visit. All ocular AEs will be followed until resolution, stabilization, or return to baseline. In these instances, additional information may be requested by ImmunoGen to adequately categorize the nature of the toxicity.

All SAEs will be followed until they resolve, stabilize or return to baseline, regardless of time from last dose or last visit.

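### Adverse-event recording has conflicting end points, and a new event starting more than 30 days after the last dose counts as a TEAE only if the patient is dosed again

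*SAP*

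**What the plan says.** Four places tell sites when adverse-event recording ends, and they do not agree.

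- **Protocol 8.1** anchors on the last study treatment; its wording is "monitored continuously throughout the study from the time of informed consent until 30 days after the", followed by that anchor. Section 8.1.1.1 repeats this for AEs and 8.2.1 for SAEs.
- **Protocol 5.7** says "the period of safety observation extends from the time of informed consent until the 30-Day Follow-up visit", with an exception where further safety follow-up is requested under 9.3. Section 9.3.1 times the visit: "A 30-Day Follow-up visit will occur 30 days (+14 days) after last dose of MIRV".
- **Protocol 5.6.1** says "Any AEs experienced up to the point of discontinuation and 30 days thereafter must be documented". The anchor here is discontinuation, not the last dose.
- **Protocol Table 2** runs the AE row for as long as the patient is on study and gives no day count.

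For counting, SAP 6.2 says "TEAEs are defined as AEs with an onset date on or after the first dose of MIRV, and within 30 days of the last dose". That same sentence closes the window earlier if new anticancer treatment starts.

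Dosing can be interrupted for longer than that window. The general trigger for discontinuation (Table 3 footnote, 5.5.1.1) is "Failure to meet retreatment criteria within 1 cycle (21 days) after the missed dose due to insufficient recovery from a treatment-related toxicity", except where toxicity-specific guidance says otherwise. For eyes, 5.5.2.2 says "Treatment with MIRV may resume if ocular symptoms improve to Grade 1 or baseline within 28 days of the next scheduled MIRV dose". Sections 5.5.2.2 and 5.5.6 let the sponsor and investigator agree to go beyond these limits in patients with clinical benefit, and state no upper bound. Section 9.2 places the EOT visit within 7 days of the decision to discontinue.

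**The concern.** A window anchored on the last dose works when treatment ends soon after that dose. Here a patient can be held, still on study treatment and still being assessed, after day 30. While the hold lasts, the site cannot know whether the dose already given will prove to be the last one, so it cannot tell whether the 8.1 recording period has closed.

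The same uncertainty carries into the tables. A new event on day 40 is a TEAE if dosing later resumes, because the last dose then moves forward. It is not a TEAE if dosing never resumes. Classification depends on a decision taken after the event, and those who lose events include patients stopped because a toxicity did not recover. The trial has no control arm and no data monitoring committee, so its TEAE tables are the main summary of its own safety data. In about 110 patients, a few events can move a low-frequency rate.

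**Working it through.** The documents print no figure for this, so there is none to reproduce. Count days from the last dose as day 0.

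**Inputs.** Cycle length 21 days (Protocol 4.1.2). General hold 21 days after the missed dose (Table 3 footnote). Ocular hold 28 days from the next scheduled dose (5.5.2.2). EOT visit up to 7 days after the decision (9.2). 30-Day visit at 30 (+14) days (9.3.1). TEAE window 30 days (SAP 6.2). Half-life 115.1 hours and 12% stopping for a TEAE on MIRV in the earlier Phase 3 trial (1.6.2). Planned enrolment about 110 (10.1).

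**Hold limits and gap**

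| | General hold | Ocular hold (5.5.2.2) |
|---|---|---|
| Limit = 21 + hold | 21 + 21 = day 42 | 21 + 28 = day 49 |
| Days outside TEAE window = limit − 30 | 12 (days 31–42) | 19 (days 31–49) |
| Latest EOT visit = limit + 7 | day 49 | day 56 |

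**End of recording for a patient stopped at the limit**

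| Source | General hold | Ocular hold |
|---|---|---|
| 8.1, 8.1.1.1, 8.2.1 | day 30 | day 30 |
| 5.7 with 9.3.1 | day 30 to 44 | day 30 to 44 |
| 5.6.1 = limit + 30 | day 72 | day 79 |
| Table 2 | no day count | no day count |

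A 30-Day visit held at its latest, day 44, covers the whole general hold (42 < 44) but leaves 49 − 44 = 5 days of the ocular hold. The 30-Day visit can also fall before the EOT visit.

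**Sensitivity to the ocular wording.** Table 5 can be read as counting how long symptoms last. With onset on day s, the limit is then s + 28, which is below 49 for any s before day 21. It still passes day 30 whenever s is later than day 2. The gap shortens on that reading but does not disappear.

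**A new event on day 40, followed through the plan.** Section 5.6.1 requires it to be recorded; 8.1 does not if no further dose is given. If recorded, it enters the all-AE listing in SAP 6.2. Without re-dosing it enters no TEAE table, including the ocular, neuropathy and pneumonitis groups. With re-dosing, and no new anticancer treatment before onset, it enters them.

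**Other windows in the SAP.** The death table (6.2) and the Grade 3 or higher laboratory summary (6.3) each cover time on treatment as well as the 30 days after the last dose. The TEAE definition has no such on-treatment limb. If a hold counts as on treatment, a death on day 40 from a new event would be in the death table while its Grade 5 event would be missing from the table of TEAEs leading to death.

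**Length of the window.** 115.1 / 24 = 4.80 days. 30 / 4.80 = 6.3 half-lives, which leaves 0.5^6.3, about 1.3% of the conjugate.

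**Scale.** 0.12 × 110 = 13.2, so about 13 patients stopping for a TEAE if the earlier rate carries over. The share stopped after a hold running past day 30 is not given. Assuming 10% to 50%, the result is 13.2 × 0.10 = 1.3 to 13.2 × 0.50 = 6.6, or about 1 to 7 patients.

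**The case against.** The strongest defence is that thirty days from last exposure is a reasonable pharmacological window, at over six half-lives, and that little of importance falls outside it. The toxicity that prevents the day-21 dose normally begins before day 30, so it appears in the TEAE, related-TEAE and drug-withdrawal tables. Protocol 8.1 still accepts unsolicited related SAEs reported later. Section 9.3.1 follows ocular AEs and SAEs until they resolve, stabilise or return to baseline. Recorded AEs and all deaths are listed. Section 5.7 is not a hard stop, because it allows for requested follow-up. The 12% covers every TEAE discontinuation, including events that stop treatment outright without a hold.

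All of this stands, and it rules out several stronger readings that a reader might infer:

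- **That late events are neither collected nor counted.** Section 5.6.1 requires collection and Table 2 can be read that way. What the text supports is contradictory collection.
- **That 30 days is too short.** The fault is the mismatch of anchors and the missing on-treatment limb, not the length.
- **That the defining toxicities disappear from the tables.** Only new-onset events after day 30 are lost.
- **That these tables are the only safety evidence for the drug.** Protocol 1.6.2 reports a randomised comparison and 1.6.3 cites 455 patients previously treated with single-agent MIRV.

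The defence does not settle which end point a site should follow, or why the same event is treatment-emergent or not according to a later dosing decision. Non-serious AEs and unrelated SAEs with onset after day 30 also have no backstop under 8.1 and 8.2.1.

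**Conclusion.** The inconsistency is real and worth correcting, with a modest effect. The recording end point for one patient can be day 30, day 30 to 44, or day 72 to 79, depending on the section read. New-onset events in days 31–42 (general hold) or up to 31–49 (ocular hold, on the 5.5.2.2 wording) are inconsistently collected. They are excluded from every TEAE table when the patient is not dosed again. TEAE, serious TEAE and Grade 3 or higher TEAE counts can therefore be slightly understated; the documents do not show that they will be.

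The number affected is unknown and probably small. The figure of 13 of 110 is a rough ceiling for patients stopped for a TEAE, and assumes that the earlier trial's 12% applies here. Days 42 and 49 assume that the next dose was due on day 21 and that no extension was agreed; an agreed extension lengthens the gap.

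**What to change.** 1. Reconcile Protocol Table 2, 5.6.1, 5.7, 8.1, 8.1.1.1 and 8.2.1 and SAP 6.2 to one end point for AE and SAE collection.
2. Add an on-treatment limb to the TEAE definition in SAP 6.2: onset from first dose through the later of 30 days after the last dose and the EOT visit, or to the start of new anticancer therapy if that is earlier.
3. Use the same end point for the death table (SAP 6.2) and the Grade 3 or higher laboratory window (SAP 6.3).
4. Reconcile the timing of the 30-Day Follow-up visit with that of the EOT visit.

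No dose, hold or stopping rule changes. The cost is protocol and SAP wording; SAP 1.1 allows the plan to be modified before final database lock. A few more events would be recorded and counted, so reported safety rates would become slightly less favourable.
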